#### Endpoints

For the primary analysis, we will use accepted measures of decreased eGFR. We have selected 30% decline in eGFR or ESRD for our primary outcome based on recommendations from a joint NKF-FDA workshop, which concluded that this should be considered as an alternative CKD endpoint for clinical trials [Inker 2014]. Specifically, in a pooled cohort of 850,096 individuals with eGFR  $\geq 60$  mL/min/1.73 m^2, a decline in eGFR  $\geq 30\%$  over 3 years of follow-up was associated with a hazard ratio of 7.0 for developing ESRD over the following decade. In secondary analysis, we will consider the more stringent endpoints of 40% decline in eGFR and development of eGFR  $< 60$  mL/min/1.73m^2. We will use the CKD Epidemiology

Collaboration (CKD-EPI) creatinine equation to estimate GFR, as it has been demonstrated to be more accurate than other creatinine-based formulas in both the general population and in HIV-infected cohorts [Matsushita 2010; Levey 2015; Inker 2012; Gagnieux-Brunon 2012; Bhagat 2013]. The CKD-EPI creatinine equation had statistically significantly higher accuracy and less bias than the cystatin C equation in HIV-infected persons [Inker 2012].

Albuminuria will be quantified by ACR calculated as urinary albumin in mg/dL divided by urinary creatinine in g/dL. Albuminuria is an easily assessed marker of kidney damage, which may precede eGFR decline, and is strongly linked to adverse clinical outcomes [Gerstein 2001]. Even at levels of albuminuria  $>30$  mg/g, persons are at increased risk for CVD events and all-cause mortality [Gerstein 2001; Wyatt 2010; Wyatt 2011]. We will use the ACR as a measure of albuminuria, as it is widely available in clinical practice and recommended by the IDSA Clinical Practice Guideline for CKD in HIV-Infected persons [Lucas 2014]. The ACR from a random urine sample is simple to obtain, correlates well with data from 24-hour urine collections, but is more practical and less prone to error than a 24-hour collection [Eknayan 2003].

#### Data Analysis Plan

*Aim 1A: Determine whether pitavastatin 4mg daily is associated with a lower incidence of  $\geq 30\%$  eGFR decline in HIV-infected persons.* We will use an intention-to-treat approach for Aim 1. Descriptive statistics for participant characteristics will be presented by randomization assignment. The percent change in eGFR from baseline at study visits at 1, 2, and 4 years post-randomization, separately, will be calculated as follow-up eGFR minus baseline eGFR divided by baseline eGFR. For our primary analysis, the CKD endpoint will be a decline in eGFR  $\geq 30\%$  from the baseline visit or incident ESRD. The percentage of participants randomized to pitavastatin and, separately, placebo having a decline in eGFR  $\geq 30\%$  will be calculated at each follow-up visit. Additionally, the cumulative proportion of participants with  $\geq 30\%$  decline in eGFR throughout follow-up will be calculated by randomization arm and differences in these percentages of participants reaching the endpoint during follow-up will be compared using a chi-square test. We will assess these differences using logistic regression adjusted for key risk covariates as a confirmatory analysis. Additionally, we will evaluate time-to-event using interval censored regression models. Interval censored regression models are proposed as we do not know the exact date an individual reaches the CKD endpoint - only that it occurred between two visits.

#### Sample Size

We will enroll a sample size of at least 2500 participants. This sample size will provide adequate statistical power to achieve our aims. We anticipate an annual event rate of 2.5% based on previous reported results [Lucas 2007; Lucas 2008]. Therefore, over 4 years, we anticipate 10% of participants will meet our primary outcome of eGFR decline. As we do not know the exact incidence of eGFR decline, we provide the minimal detectable difference based on this event rate and also for 8% and 15% incidence of eGFR decline (ie, annual event rates of 2% and 3.75%, respectively). Based on sample size of 2500 participants (50% randomized to pitavastatin and 50% placebo), a two-tailed alpha error of 5% and assuming 5% of participants will be lost during follow-up, we will have 90% statistical power to detect clinically relevant differences in the cumulative incidence of eGFR decline across randomization arms. For example, if 10% of participants randomized to placebo develop our primary endpoint over the 4-

year follow-up period, we will have 90% power to detect an absolute reduction in incidence of 3.6% associated with pitavastatin (10% in placebo vs. 6.4% in pitavastatin arm; **Table 1**). Given that albuminuria is anticipated to be a more frequent endpoint than  $\geq 30\%$  eGFR decline, we will have 90% power to detect clinically relevant differences in the percentage of participants developing this outcome measure. Previous RCTs of pitavastatin in individuals with diabetes and persons with hyperlipidemia demonstrated a 52% and 67% reduction in measures of albuminuria, respectively [Nakamura 2005; Yagi 2011]. Although we expect to see at least a 50% reduction in albuminuria in the pitavastatin group (from 15% to 7.5%) and a modest increase in prevalence of albuminuria in the placebo group [Szczech 2010], we will be powered to detect smaller differences.

Table 1. Minimal detectable difference in incidence of CKD endpoint in REPRIEVE participants randomized to pitavastatin vs placebo.

	Proportion of control population developing CKD		
Aim 1A eGFR decline	8%	10%	15%
90% statistical power	3.2%	3.6%	4.3%
80% statistical power	2.6%	3.2%	3.5%
	Proportion of control population with albuminuria		
Aim 1B % with albuminuria	15%	20%	25%
90% statistical power	4.3%	4.9%	5.4%
80% statistical power	3.8%	4.3%	4.7%

**OBJECTIVE 2: Assess whether the effect of pitavastatin on CKD is stronger in high-risk groups defined by older age, black race, hypertension, lower CD4 cell counts, or the use of TDF-containing regimens.** We will divide the cohort based on the median age to evaluate differences between the groups above and below the median age. Similar dichotomous approaches will be taken for black race, hypertension (systolic blood pressure  $\geq 140$  mmHg, diastolic blood pressure  $\geq 90$  mmHg or antihypertensive medication use), and TDF-containing regimens. Within each sub-group studied, participant characteristics will be calculated by randomization assignment (pitavastatin or placebo). The percentage of participants developing  $\geq 30\%$  eGFR decline and separately, with ACR  $> 30$  mg/g during follow-up will be calculated for participants randomized to pitavastatin and, separately, their counterparts randomized to placebo. The statistical significance of differences within sub-groups will be calculated using interval censored regression models and chi-square tests as described in Aim 1 above. We will use multiplicative interaction terms (eg, black race \* pitavastatin) to assess differences in the effect of pitavastatin on CKD across sub-groups. We will evaluate CD4 count as a continuous variable to determine if there is a threshold below which statin therapy has greater benefit for kidney function. We will model the interaction between pitavastatin versus placebo and CD4 count as a continuous variable with interval censored regression models and logistic regression for the cumulative incidence [Howard 2011].

**OBJECTIVE 3: To determine whether the effect of pitavastatin on kidney function is mediated through anti-inflammatory effects.** This analysis will follow the traditional case-cohort design. The case-cohort design combines the advantages of cohort studies and case-control analyses. In a case-cohort design, the comparison group is not defined on the basis of the "absence" of the outcome ( $\geq 30\%$  eGFR decline or ACR  $> 30$  mg/g; as in a traditional "case-control" study design). This is advantageous for the following reasons: 1) the strategy allows for studying multiple endpoints using the same "control" group (ie, the sub-cohort); 2) it bypasses a certain degree of arbitrariness unavoidable when attempting to define the comparison group intended to include only "non-cases" (ie, the inclusion of "false negatives"); 3) the strategy allows a random sample of the cohort for valid cross-sectional comparisons (eg, the association between baseline ACR and biomarkers of CKD and systemic and vascular inflammation and oxidative stress in the cohort random sample); and 4) it allows calculation of hazard ratios using survival models rather than relying on logistic regression and calculation of odds ratios.

The distribution of biomarkers at baseline and during follow-up will be graphed. For biomarkers that are not normally distributed, an appropriate transformation will be performed (eg, log transformation). Mean baseline and change in the levels of these biomarkers will be calculated for participants who experience a  $\geq 30\%$  decline in eGFR and the sub-cohort. Differences will be calculated using ANOVA with weighting to account for the probability of selection into the sub-cohort. Next, we will calculate the association between biomarkers of CKD, systemic and vascular inflammation and oxidative stress with CKD progression using a pseudo-likelihood, weighted Cox regression model. Using the approach of Barlow and Prentice for case-cohort analysis, we will calculate the hazard ratio for a  $\geq 30\%$  decline in eGFR associated with each biomarker separately. Initial models will control for age, race, and sex. Subsequent models will include further adjustment for systolic blood pressure, total and HDL-cholesterol, cigarette smoking, waist circumference, and baseline eGFR and ACR. A final model will include further adjustment for  $\log_{10}$  HIV RNA load and CD4 $^{+}$  T-cell counts.

Next, we will conduct a mediation analysis to test whether pitavastatin lowers the incidence of  $\geq 30\%$  eGFR decline by reductions in biomarkers assessed. To address mediation that pitavastatin will reduce the incidence of eGFR decline through improvements in systemic and vascular inflammation and oxidative stress, we will apply the regression technique described by Judd and Kenny and elaborated by MacKinnon [Judd 1981; MacKinnon 1994]. The technique, will account for each biomarker separately and for all biomarkers simultaneously (mediators) using two regression equations ([Table 2](#)). Y is the outcome result (eg, eGFR decline  $\geq 30\%$ ),  $X_p$  is randomization to pitavastatin versus placebo and  $X_i$  represents the k biomarkers, our purported mediators. The total effect of pitavastatin on the outcome (measured by the coefficient,  $\tau$ ) is the sum of direct effect ( $\tau'$ ) of treatment and the mediated, or indirect, effects. The assessment of the amount of change in these biomarkers mediating the effect of pitavastatin on eGFR decline will be addressed by considering two multivariable regression models (see [Table 2](#)). First, a regression model that estimates the decreased risk of a  $\geq 30\%$  eGFR decline with pitavastatin without mediating risk factors but considering other risk factors (eg, age, race, sex, hypertension) and a second Cox regression model that further makes adjustment for the mediating risk factor (ie, biomarkers of inflammation and oxidative stress). For these analyses, the parameter of interest (ie, log hazard ratio) is not the impact of pitavastatin on outcomes, but rather the difference in the estimated impact of pitavastatin

between the two models ( $\tau' - \tau$ ), which serves as a direct measure of the degree to which the effect of pitavastatin is due to improvements in these biomarkers. Whether the biomarkers "significantly" mediate the benefits of pitavastatin can be addressed by creating empirical confidence intervals around the change in its coefficient. Confidence interval of the change in the coefficient associated with the disparity will be calculated using bootstrap methods.

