*Enrollment will be completed in 30 months:* Given the total study duration of 6 years after enrollment has begun, individual participant follow-up will range from 3.5 to 6 years, with a median follow-up of 4.75 years. REPRIEVE (A5332) will be conducted at approximately 100-130 sites including the majority of all domestic ACTG sites, and selected non-US ACTG sites as well as protocol specific sites. The assumed enrollment period of 30 months requires an average enrollment rate of 2.2 participants per site per month. Given a staggered rate of site activation, actual site enrollment will need to be between 3 to 4 participants per site per month. This enrollment rate is consistent with enrollment rates observed in recent large ACTG trials and with the expectations of the study sites based on a site survey. Further, a site survey conducted in early 2014 has suggested broad availability of the target study population. As of May 29, 2014, of sites queried, a total of 153 sites have expressed an interest in participating in REPRIEVE (A5332) and estimated being able to enroll 10,551 out of an estimated pool of 46,395 eligible participants.

*An annual 5% loss to follow-up rate:* Since 1999, the ACTG has actively followed a large cohort of individuals on a limited visit schedule. During that time, the annual rate of lost to follow up was observed to be around 5.6%. We believe that we will be able to achieve a rate lower than this in REPRIEVE (A5332) since participants may also be receiving active treatment. Indeed, while this conservatively high estimate maintains power of study even in the event of 25% rate of loss over the duration of the study, it is desired that the observed rate will be no more than 15% over 6 years.

*Estimated treatment cross-over rates of 10%:* REPRIEVE (A5332) is powered to detect a statin effectiveness equating to a HR of 0.70. The influence of treatment switching (crossover) on the effectiveness of statin treatment for the prevention of MACE and impact of this crossover on the power of the REPRIEVE (A5332)

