the outcome of MACE. To assess power for interaction effect, methods described in [VanderWeele 2012] will be used under the following assumptions: 4.9% of men with low immune activation will have a qualifying MACE outcome; the main effect odds ratios (OR) for sex and immune activation are each 2.1 (eg, 4.9% MACE in one group compared with 9.8% in the other); a multiplicative interaction OR of 1.33; association between sex and high/low immune activation of 1.33; and 22% female enrollment. Based on these assumptions and using a significance level adjusted to 0.0167, the statistical power for additive interaction effect (eg, as excess in relative risk attributed to interaction) is estimated as 80%. Testing for interaction effects and covariate adjusted models will use multivariable logistic regression (for the primary outcome) and Cox proportional hazards regression (for the secondary, time- to-event formulation outcome).

*Hypothesis C)* *Statins will decrease levels of immune activation markers to a greater extent in HIV-infected women versus men.* The outcomes being tested in this sub-objective are the changes from pre-treatment to 1 year of follow-up of the immune activation markers tested. For this hypothesis, statistical interactions of sex and treatment effects will be tested using linear (log transformed as indicated) models, which can also incorporate covariate adjustment. With estimates of 5% per year loss to follow-up, the effective sample size for this sub-aim is 5174 persons. For the biomarker sCD14, standard deviation of the outcome measure for this sub-aim is estimated assuming standard deviation of 1-year measurements same as baseline and intra-person correlation of 0.65. Further, assuming under additivity a 125 ng/mL effect of sex on sCD14 differences at 1 year and the same effect of statins on sCD14 differences at 1 year, there will be 80% power to detect an additive interaction effect of 220 ng/mL.

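### Appendix V's 90% power assumes 5% total loss over 4 years against the parent trial's 5% per year; at the parent's rate power for 10% vs 6.4% is about 84–86%, and Table 1 does not apply even the 5%.

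*Protocol*

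**What the plan says.** Protocol, Appendix V, Sample Size, sets at least 2500 participants, equal allocation and a two-sided 5% test. The time frame is four years: "over 4 years, we anticipate 10% of participants will meet our primary outcome of eGFR decline". The loss allowance is "assuming 5% of participants will be lost during follow-up", with no annual qualifier and no source. On that basis, "we will have 90% power to detect an absolute reduction in incidence of 3.6% associated with pitavastatin". The proportions behind this difference are 10% for placebo and 6.4% for the active arm. Table 1 then lists detectable differences at 90% and 80% power for eGFR decline and for albuminuria.

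The Appendix V Data Analysis Plan compares, by chi-square test, the cumulative proportion reaching the endpoint over visits at years 1, 2 and 4. An interval-censored time-to-event model is added.

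The parent trial (Protocol, section 9.4.1) lists among its assumptions "An annual 5% loss to follow-up rate". It reports about 5.6% per year in an ACTG cohort, expects to do better, describes 5% as conservatively high, and wants no more than 15% lost over 6 years.

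Appendix V draws its participants from ACTG sites only and collects its samples at parent-trial visits.

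**The concern.** One protocol uses two loss rates for overlapping people on the same visit schedule. Appendix V allows 5% over four years. The parent's planning rate implies 18.5% over the same period, and even its hoped-for ceiling implies about 10%. Nothing in Appendix V explains why kidney participants would be retained so much better than the trial they belong to.

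The stated power and detectable difference are what a reader would use to judge how informative a null kidney result is. If they rest on an unexplained, more favourable retention figure, the study looks somewhat more sensitive than the protocol's own planning supports.

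**Working it through.** **Inputs.** 1250 per arm, two-sided α = 0.05, p₁ = 0.10, p₂ = 0.064, 4 years, visits at years 1, 2 and 4 (Appendix V). Loss of 5% in total (Appendix V), 5% per year, or 15% over 6 years (section 9.4.1).

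**Formula.** Pooled two-proportion z test, equivalent to chi-square, with p̄ = 0.082 and n evaluable per arm:

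power = Φ{ [ |p₁−p₂| − 1.96·√(2p̄(1−p̄)/n) ] / √[ (p₁(1−p₁)+p₂(1−p₂))/n ] }

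**Step 1: the plan's own figure.** n = 1250 × 0.95 = 1187.5. Power = Φ[(0.0360 − 0.0221)/0.01124] = 89.3%. The difference detectable with 90% power is 3.64 points, which rounds to the stated 3.6. The headline therefore reproduces under its stated inputs.

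**Step 2: the parent's loss, counting only people who reach year 4.**
- 5% per year: 0.95⁴ = 0.8145, so 18.5% are lost and n = 1018. Power = Φ[(0.0360 − 0.0238)/0.01213] = 84.2%; 90%-power detectable difference 3.9 points. Taking the loss linearly (20%, n = 1000) gives 83.6%.
- 15% over 6 years: 0.85^(4/6) = 0.897, so 10.3% are lost and n = 1122. Power 87.5%; detectable difference 3.7 points.

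**Step 3: the parent's loss, keeping outcomes seen before loss.** Assume a constant event rate (a quarter of events by year 1, a quarter in year 2, half in years 3–4) and loss unrelated to outcome. An event is seen if the person is still present at the next visit.
- 5% per year: fraction of events seen = 0.25×0.95 + 0.25×0.9025 + 0.5×0.8145 = 0.870. With all 1250 per arm in the denominator, the observed proportions are 8.7% vs 5.6% and power is 86.1%. With only the 1187.5 per arm who have at least one follow-up visit, they are 9.2% vs 5.9% and power is 86.2%.
- 15% over 6 years: fraction seen = 0.25×0.973 + 0.25×0.947 + 0.5×0.897 = 0.929; power 88.4%.

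| Loss assumption | Year-4 completers only | Pre-loss visits kept |
|---|---|---|
| 5% in total | 89.3% | – |
| 15% over 6 years | 87.5% | 88.4% |
| 5% per year | 84.2% | 86% |

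**Step 4: Table 1.** Solving the same formula for the detectable difference, in percentage points:

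| Row (control rates) | Printed | No loss, 1250/arm | 5% loss, 1187.5/arm |
|---|---|---|---|
| eGFR, 90% power (8/10/15%) | 3.2 / 3.6 / 4.3 | 3.2 / 3.6 / 4.3 | 3.2 / 3.6 / 4.4 |
| Albuminuria, 90% power (15/20/25%) | 4.3 / 4.9 / 5.4 | 4.3 / 4.9 / 5.4 | 4.4 / 5.1 / 5.5 |
| eGFR, 80% power (8/10/15%) | 2.6 / 3.2 / 3.5 | 2.8 / 3.1 / 3.8 | 2.9 / 3.2 / 3.9 |
| Albuminuria, 80% power (15/20/25%) | 3.8 / 4.3 / 4.7 | 3.8 / 4.3 / 4.7 | 3.9 / 4.4 / 4.8 |

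Both 90% rows match no loss. The 80% eGFR row fits neither sample size throughout. The table also disagrees with itself: at a 15% control rate and 80% power it prints 3.5 for eGFR and 3.8 for albuminuria, although at 90% power it prints 4.3 for both.

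**The case against.** The strongest reply is that the gap is small and the parent's rate is deliberately pessimistic. Section 9.4.1 says so, and at its hoped-for retention power is 87–88%, within about two points of what Appendix V's inputs give. This stands as a limit on the size of the point. It does not remove the inconsistency, because even the hoped-for retention implies about twice Appendix V's loss.

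Second, the endpoint is cumulative, so someone lost after year 1 or 2 has already contributed. A reader might infer that true power is simply 84%. The documents do not support that as a single figure: 84% treats everyone lost before year 4 as contributing nothing, and keeping earlier visits gives about 86%. Appendix V does not say which applies in the chi-square test.

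Third, a reader might take the kidney cohort and the parent as identical, or take Appendix IV as confirming 18.5% loss. Neither is right. The kidney participants are a subset from ACTG sites. Appendix IV does use an annual rate ("With estimates of 5% per year loss to follow-up, the effective sample size for this sub-aim is 5174 persons"), but it applies it to a one-year change, so its loss there is also 5% and it sets no four-year convention.

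Fourth, 2500 is a floor, and the kidney aim is ancillary. Both are true, but the stated power is calculated at 2500. Holding 90% power for 3.6 points at 5% per year, counting completers only, would need about 2994 participants (2 × 1219 = 2438 evaluable, divided by 0.8145). No such target is set.

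Finally, Appendix V says the true incidence is uncertain, and its 90% row already runs from 3.2 to 4.3 points across the rates it tabulates. A move from 3.6 to 3.9 lies inside that range, which keeps the severity modest.

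**Conclusion.** The loss assumptions conflict, and Appendix V does not explain its lower figure. With 2500 participants, power for 10% vs 6.4% is 89% at 5% total loss, about 87–88% at the parent's desired retention and about 84–86% at its planning rate. The overstatement is therefore roughly 2 to 6 points against the stated 90%, and power stays above 80% throughout. The 86% and 88% figures assume a constant event rate and loss unrelated to outcome; the 84% assumes lost participants contribute no outcome.

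This is a disagreement between planning assumptions, not a miscalculated headline, since the 90% reproduces to within a point from its own inputs. A reader might also infer that the 5% was an annual rate written as a total. That is possible, but nothing in the documents shows it.

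Table 1 needs correction whichever loss rate is chosen: it appears not to include the stated 5%, and its 80% eGFR row is wrong under either sample size. Severity is minor to moderate.

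**What to change.** In Appendix V, Sample Size:

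1. Replace the 5% total loss with the parent's 5% per year, or keep 5% in total and give the reason for it.
2. If 5% per year is adopted, restate power for 10% vs 6.4% as about 84–86% and the 90%-power detectable difference at 10% incidence as up to 3.9 points.
3. State whether participants lost before year 4 count in the chi-square test, and how outcomes seen at years 1 and 2 are used for them. This decides which end of the range applies.
4. Recompute every cell of Table 1 with the chosen loss. If 5% in total is kept and justified, the 90% rows become 3.2/3.6/4.4 and 4.4/5.1/5.5, and the 80% eGFR row about 2.9/3.2/3.9.

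The cost is wording, one table and a slightly less favourable stated power. No patients, visits or samples are added.

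### Kidney ancillary study, Table 1: two 80%-power cells for eGFR decline carry about 72% and 71% power, and one contradicts the albuminuria row; the base case holds

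*Protocol*

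**What the plan says.** Appendix V, Sample Size, sets out one set of inputs for the whole of Table 1: at least 2500 participants, "50% randomized to pitavastatin and 50% placebo", "a two-tailed alpha error of 5" per cent, and "assuming 5% of participants will be lost during follow-up". The Data Analysis Plan for Aim 1A names the test for the cumulative proportion: "differences in these percentages of participants reaching the endpoint during follow-up will be compared using a chi-square test".

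The base assumption is that 10% of participants reach the eGFR endpoint over four years. Because the true incidence is unknown, the section gives detectable differences "also for 8% and 15% incidence of eGFR decline (ie, annual event rates of 2% and 3.75%, respectively". The prose claims 90% power and gives one worked example, "10% in placebo vs. 6.4% in pitavastatin arm", a difference of 3.6 points.

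Table 1, titled "Minimal detectable difference in incidence of CKD endpoint in REPRIEVE participants randomized to pitavastatin vs placebo", then prints, in percentage points:

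| Row | Control proportions | 90% power | 80% power |
|---|---|---|---|
| eGFR decline (Aim 1A) | 8 / 10 / 15% | 3.2 / 3.6 / 4.3 | 2.6 / 3.2 / 3.5 |
| Albuminuria (Aim 1B) | 15 / 20 / 25% | 4.3 / 4.9 / 5.4 | 3.8 / 4.3 / 4.7 |

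**The concern.** The discrepancy is visible before any calculation. Both rows contain a column for a 15% control proportion. A detectable difference between two proportions depends on sample size, alpha, power and the control proportion, not on what the endpoint is called. At 90% power the two rows agree at 4.3 points. At 80% power they print 3.5 and 3.8. Both cannot be right.

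EGFR decline is the ancillary study's primary outcome, and the 8% and 15% columns are there to show what happens if the 10% assumption is wrong. Suppose the trial gives a null result at one of those incidences. A reader of the printed table would take the chance of missing a 2.6- or 3.5-point effect to be 20%, when it is 28% to 29%.

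**Working it through.** **Inputs.** N = 2500, 1:1, two-sided alpha 0.05 (z = 1.96), 5% loss, all from Appendix V, Sample Size. Evaluable per arm: 2500 × 0.95 / 2 = 1187.5. Without loss: 1250.

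**Formula** (normal approximation to the chi-square test, pooled variance under the null). With control proportion p1, difference d, p2 = p1 − d and p̄ = (p1 + p2)/2:

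- s0 = √[2 p̄(1 − p̄)/n]
- s1 = √{[p1(1 − p1) + p2(1 − p2)]/n}
- power = Φ[(d − 1.96 s0)/s1]

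**The plan's own example first.** For 10% vs 6.4% at n = 1187.5: s0 = 0.01126, s1 = 0.01124, (0.036 − 0.02207)/0.01124 = 1.240, power about 89%. At n = 1250 it is 90.7%. The example reproduces, and so does the 10% cell at 80% power (10% vs 6.8%: 80.3% after loss).

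**The two cells in question**, at n = 1187.5:

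- 8% vs 5.4%: s0 = 0.01026, s1 = 0.01025, (0.026 − 0.02011)/0.01025 = 0.575, power 71.7%. At n = 1250: 73.9%.
- 15% vs 11.5%: s0 = 0.01391, s1 = 0.01390, (0.035 − 0.02727)/0.01390 = 0.556, power 71.1%. At n = 1250: 73.3%.

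**Could method or rounding explain them?** After loss, the unpooled test gives 71.8% and 71.2%, the arcsine version 72.1% and 71.2%, and the continuity-corrected version 68.9% and 69.0%. Taking each printed cell at the top of its rounding interval (2.65 and 3.55 points) gives 73.5% and 72.4%. To have 80% power at the printed differences, the study would need 1451 and 1472 evaluable per arm, which is 1451/1187.5 = 1.22 and 1472/1187.5 = 1.24 times what is planned.

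**Every cell, solved for the detectable difference** (percentage points):

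| Row, power | Control | Printed | n = 1187.5 | n = 1250 | Power of printed value after loss |
|---|---|---|---|---|---|
| eGFR, 90% | 8% | 3.2 | 3.247 | 3.17 | 89.0% |
| eGFR, 90% | 10% | 3.6 | 3.64 | 3.56 | 89% |
| eGFR, 90% | 15% | 4.3 | 4.44 | 4.33 | 88.0% |
| eGFR, 80% | 8% | **2.6** | 2.848 | 2.78 | **71.7%** |
| eGFR, 80% | 10% | 3.2 | 3.19 | 3.11 | 80.3% |
| eGFR, 80% | 15% | **3.5** | 3.87 | 3.78 | **71.1%** |
| Albuminuria, 90% | 15% | 4.3 | 4.44 | 4.33 | 88.0% |
| Albuminuria, 90% | 20% | 4.9 | 5.048 | 4.93 | 88.1% |
| Albuminuria, 90% | 25% | 5.4 | 5.53 | 5.39 | 88.6% |
| Albuminuria, 80% | 15% | 3.8 | 3.87 | 3.78 | 78.4% |
| Albuminuria, 80% | 20% | 4.3 | 4.40 | 4.29 | 78.2% |
| Albuminuria, 80% | 25% | 4.7 | 4.81 | 4.69 | 78.2% |

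**Which denominator was used?** Leave the two bold cells aside. Of the other ten, seven agree with the printed digit only at 1250 per arm: all six albuminuria cells and the eGFR 15% cell at 90% power. Two agree at either n (eGFR 90% power, 8% and 10%). One, the eGFR 10% cell at 80% power, agrees only at 1187.5. The table therefore mixes denominators although the text states one. The cost is about 0.1 point per affected cell, or roughly 2 points of power.

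**The case against.** The strongest reply is that nothing important rests on these cells. The prose claims 90% power, and its example gives about 89% after loss. The 90% cells at the same two incidences hold nearly as well (89.0% at 8%, 88.0% at 15%). No sentence in the section relies on the 80% row. The 8% and 15% columns are alternatives to the base case, and 2500 is described as a minimum. The fault lies in an ancillary appendix, and follow-up urine collection is limited to participants enrolled at ACTG sites before 01/01/2018 (Section 6.1 footnote and Section 6.3.6), so corrected cells would not guide recruitment for it. All of that stands, and it sets the priority. It does not make the cells correct.

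A reader might infer that the kidney study is underpowered for its primary endpoint, or that 2500 is too few. The documents do not support that: at 10% control incidence, 3.6 points has about 89% power and 3.2 points has 80.3%.

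A reader might also conclude that the two cells were computed one-sided. A one-sided 5% test at 1187.5 per arm does give detectable differences of 2.55 and 3.46, which round to the printed 2.6 and 3.5 (power 81.3% and 80.8%). But the text says two-tailed, and the 10% cell in the same row fits only a two-sided test (one-sided it would be 2.85). This is a plausible origin for the error and remains inference; it does not defend the figures.

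**Conclusion.** Two cells of Table 1 are wrong as written. At 80% power the eGFR entries for 8% and 15% control incidence are too small by about 0.2 and 0.4 points, and the printed differences carry about 72% and 71% power. The 15% entry also contradicts the albuminuria row of the same table. The uneven use of the 5% loss is a smaller, separate fault worth about 2 points of power. These results rest on the section's own inputs and its named chi-square test. The shortfall in the two cells persists under the other two-sided versions tried and when the loss is dropped. The base case and the prose claim of 90% power hold to within 1 to 2 points, so the sample size is not called into question. Priority: minor.

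**What to change.** Recompute Table 1 once, at about 1187 evaluable per arm, two-sided, and state that denominator under the table. In percentage points:

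| Row | 90% power | 80% power |
|---|---|---|
| eGFR decline, control 8 / 10 / 15% | 3.2 / 3.6 / 4.4 | 2.8 / 3.2 / 3.9 |
| Albuminuria, control 15 / 20 / 25% | 4.4 / 5.0 / 5.5 | 3.9 / 4.4 / 4.8 |

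Three entries lie just under a rounding boundary (2.848, 3.247 and 5.048), so round from the unrounded values or print two decimals. The printed eGFR entries at 8% (90% power) and at 10% (both powers) stay as they are. The cost is one corrected table with slightly less favourable figures. Sample size, endpoint, test and conduct do not change.
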